4.5.1 Informed Consent Forms and Screening Log

Written informed consent for participation in the study must be obtained before performing any study-related procedures. Informed Consent Forms for enrolled patients and for patients who are not subsequently enrolled will be maintained at the study site.

All screening evaluations must be completed and reviewed to confirm that patients meet all eligibility criteria before enrollment. The investigator will maintain a screening log to record details of all patients screened and to confirm eligibility or record reasons for screening failure, as applicable.

4.5.2 Eligibility at Screening

At screening, patients who fail to meet any laboratory inclusion/exclusion criteria or other eligibility criteria may be retested or re-screened as per the instructions in Section 4.5.2.1 and Section 4.5.2.2, respectively.

4.5.2.1 Retesting: Laboratory Inclusion/Exclusion

If a patient does not meet certain laboratory inclusion/exclusion criteria at screening, the investigator may repeat the tests once within the screening period (see Section 4.1.2 for laboratory tests and levels that can be retested). If the patient meets the laboratory eligibility criteria on the second assessment, he or she will be permitted to enter the study. It will not be considered a retesting if blood samples have to be redrawn because of sample handling problems, breakage, sample integrity, or laboratory error.

4.5.2.2 Re-screening

Re-screening refers to repeating the entire screening process. Re-screening is required if a patient has not met eligibility criteria within the original screening visit. (Note: patients who have failed two laboratory testing attempts as described in Section 4.1.2 cannot be re-screened). Patients are allowed to be re-screened only once *per cohort*. Each patient must be re-consented before re-screening occurs. It will not be considered a re-screening if blood samples have to be redrawn because of sample handling problems, breakage, sample integrity, or laboratory error.

4.5.3 Medical History and Demographic Data

Comprehensive medical and surgical history, including a comprehensive review of the patient's CSU medical history, will be collected at the Day -14 visit for both cohorts. This review will include onset of symptoms, date of diagnosis, and therapies received for CSU. In addition, history of omalizumab (Xolair®) use and reason for discontinuation will be collected.

Concomitant medical usage will be collected at all visits, including unscheduled visits. Demographic data will include age, sex, and self-reported race/ethnicity.

4.5.4 Physical Examinations

A complete physical examination should be performed at the Day -14 visit for both cohorts and should include an evaluation of the head, eyes, ears, nose, and throat, and the cardiovascular, dermatological, musculoskeletal, respiratory, GI, genitourinary, and neurological systems. Any abnormality identified at baseline should be recorded on the General Medical History and Baseline Conditions eCRF.

Subsequent examinations may be limited to detect changes in symptoms of CSU as well as directed by patient complaints regarding adverse events. Changes from baseline abnormalities should be recorded in patient notes. New or worsened clinically significant abnormalities should be recorded as adverse events on the Adverse Event eCRF.

4.5.5 Vital Signs

Vital signs will include measurements of heart rate, systolic and diastolic blood pressure while the patient is in a seated position, and temperature. Vital signs will be assessed as outlined in the Schedule of Activities in [Appendix 1](#) and during other unscheduled study visits when clinically indicated. The patients' height and weight will be measured once during the screening visit for both cohorts.

4.5.6 FricTest

For subjects who have a history of dermatographism, a FricTest® will be performed at screening (Day –14), baseline (Day 1), and Days 57 and 85 for both cohorts. The FricTest® is a flat, plastic comb with four round-ended plastic pins, 3 mm in diameter and of different lengths. The FricTest® defines provocation thresholds and severity of dermatographism (i.e., 4 pins inducing wheals defines severe dermatographism).

4.5.7 Laboratory, [REDACTED] and Other Biological Samples

Samples for the following laboratory tests will be sent to one or several central laboratories for analysis as per the Schedule of Activities in [Appendix 1](#). Laboratory tests prior to randomization and dosing may be performed locally on Day 0, if central laboratory tests are not available due to sampling handling problems, breakage, or lab error.

- Hematology: hemoglobin, hematocrit, platelet count, RBC count, WBC count, percent and absolute differential counts (neutrophils, bands, lymphocytes, monocytes, eosinophils, basophils, other cells)
- Serum chemistry: sodium, potassium, chloride, bicarbonate, glucose, BUN, creatinine, calcium, phosphorus, magnesium, total and direct bilirubin, total protein, albumin, ALT, AST, LDH, alkaline phosphatase, creatine phosphokinase, CRP, lipase, and uric acid
- Urinalysis including dipstick (pH, specific gravity, glucose, protein, ketones, blood) and microscopic examination (sediment, RBCs, WBCs, casts, crystals, epithelial cells, bacteria)
- Coagulation: INR, activated PTT, PT, fibrinogen
- Fasting lipid panel
- Viral serology
- Hepatitis B: HBsAg, total HBcAb, and hepatitis B surface antibody
- Hepatitis C antibody

█ [REDACTED]

█ [REDACTED]

- The following samples will be sent to the Sponsor or a designee for analysis:

█ [REDACTED]

- Plasma samples for PK analysis
- See the Schedule of Activities provided in [Appendix 1](#) for specific timepoints.
- Samples for the following laboratory tests will be sent to the study site's local laboratory for analysis:
- Pregnancy test

All women of childbearing potential (including those who have had a tubal ligation) will have a serum pregnancy test at screening. Urine pregnancy tests will be performed at specified subsequent visits. If a urine pregnancy test result is positive, it must be confirmed by a serum pregnancy test. Should a positive result be recorded at any time, the procedures detailed in Section [5.4.3](#) should be followed. If a local urine pregnancy test shows a positive result, then study drug will not be administered that day. Other study procedures should also be postponed and the result must be confirmed by a serum pregnancy test prior to proceeding.

- QFT or PPD (if QFT not available) and additional procedures (e.g., chest X-ray) to rule out latent or active TB per local guidelines

See the Schedule of Activities provided in [Appendix 1](#) for specific timepoints.

[REDACTED]

█ [REDACTED]

[REDACTED]

For sampling procedures, storage conditions, and shipment instructions, see the laboratory manual.

Biological samples will be destroyed when the final clinical study report (CSR) has been completed, with the following exceptions:

- Plasma samples collected for PK analysis will be destroyed no later than 5 years after the final CSR has been completed.
- Blood, urine, and serum samples collected [REDACTED] will be destroyed no later than 15 years after the final CSR has been completed.

When a patient withdraws from the study, samples collected prior to the date of withdrawal may still be analyzed, unless the patient specifically requests that the samples be destroyed or local laws require destruction of the samples. *However, if samples have been tested prior to withdrawal, results from those tests will remain as part of the overall research data.*

Data arising from sample analysis will be subject to the confidentiality standards described in Section 8.4.

4.5.8 Electrocardiograms

A single ECG recording, without artifacts, must be obtained at specified timepoints, as indicated in [Appendix 1](#). The ECG intervals (e.g., PR, QRS, QT, QTcF, and RR) and heart rate from this ECG will be entered into the eCRF. Any morphologic waveform changes or other ECG abnormalities must be documented on the eCRF.

All ECG recordings must be performed using a standard high-quality, high-fidelity digital electrocardiograph machine equipped with computer-based interval measurements. Lead placement should be as consistent as possible. ECGs for each patient should be obtained from the same machine whenever possible. ECG recordings must be performed after the patient has been resting in a supine position for at least 10 minutes prior to beginning the ECG recording. All ECGs *can be performed without specific restrictions (e.g., can be performed at any time of day, before or after dosing, fasting or fed) but* are to be obtained prior to other procedures scheduled at that same time (e.g., vital sign measurements, blood draws). Body position should be consistently maintained for each ECG evaluation to prevent changes in heart rate. Circumstances that may induce changes in heart rate, including environmental distractions (e.g., television, radio, conversation) should be avoided during the pre-ECG resting period and during ECG recording.

For safety monitoring purposes, the investigator must review, sign, and date all ECG tracings. Paper copies of ECG tracings will be kept as part of the patient's permanent study file at the site. If considered appropriate by the Sponsor, ECGs may be analyzed retrospectively at a central laboratory.

If at a particular post-dose timepoint the mean QTcF is >500 ms or >60 ms longer than the baseline value, another ECG must be recorded, ideally within the next 5 minutes, and ECG monitoring should continue until QTcF has stabilized on two successive ECGs.

The Medical Monitor should be notified as soon as possible within 24 hours. Standard-of-care treatment may be instituted per the discretion of the investigator. If a PK sample is not scheduled for that timepoint, an unscheduled PK sample should be obtained. A decision on study drug discontinuation should be made, as described in Section 4.6.2. The investigator should also evaluate the patient for potential concurrent risk factors (e.g., electrolyte abnormalities, co-medications known to prolong the QT interval, severe bradycardia).

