5.1.1.7 Cardiovascular Effects

Fenebrutinib is considered to have a low potential to cause QT interval prolongation or to directly affect other cardiovascular parameters, at therapeutic exposures. A minimal increase in QTc (7 ms or 3%) interval was noted at 45 mg/kg in the single-dose cardiovascular safety pharmacology study in telemetry-instrumented dogs. [REDACTED]

[REDACTED] There have been no fenebrutinib-related changes in ECG parameters in the 4-week or 9-month dog toxicity studies.

Analysis of ECG data from the SAD and MAD studies in healthy subjects did not demonstrate any significant increase in either QRS interval or QTcF intervals. However, cardiac safety will be evaluated in all patients at baseline and throughout this study, with routine monitoring of vital signs (including heart rate and blood pressure), routine safety ECGs, and collection of adverse events (see Section [5.1.1.7](#) and Section [5.2.1](#)).

Management of patients with sustained QTcF prolongation (QTcF that is >500 ms or >60 ms longer than the baseline value) should include recording another ECG, ideally within the next 5 minutes, and ECG monitoring should continue until QTcF has stabilized on two successive ECGs. The Medical Monitor should be notified as soon as possible within 24 hours. Standard-of-care treatment may be instituted per the discretion of the

investigator. If a PK sample is not scheduled for that timepoint, an unscheduled PK sample should be obtained. A decision on study drug discontinuation should be made, as described in Section 4.6.2. The investigator should also evaluate the patient for potential concurrent risk factors (e.g., electrolyte abnormalities, co-medications known to prolong the QT interval, severe bradycardia).

Guidelines for management of study treatment in the event in the event of cardiovascular effects in patients are provided in Section 5.1.2. Please refer to the Fenebrutinib Investigator's Brochure for further details.

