| Sustained (at least two ECG measurements > 30 minutes apart) QTcF that is > 500 ms or > 60 ms longer than the baseline value | Unless there is a clear alternative cause other than study drug, discontinue study treatment. ^c |
| Sustained absolute QTcF that is > 515 ms | Unless there is a clear alternative cause other than study drug, discontinue study treatment. ^c |
| An episode of torsades de pointes or a new ECG finding of clinical concern | Unless there is a clear alternative cause other than study drug, discontinue study treatment. ^c |
| Vascular inflammation | |
| Vasculitis | Discontinue study treatment and consult with the Medical Monitor. |

IV = intravenous; QTcF = QT interval corrected using Fridericia's formula; ULN = upper limit of normal.

Note: "Study treatment" includes study drug (fenebrutinib or placebo).

^a Any patient who discontinues study treatment should enter safety follow-up, if possible.

^b Appropriate laboratory investigations, including but not limited to cultures, should be performed to establish the etiology of any serious infection.

^c In rare circumstances, it may be acceptable to resume study drug, provided that any ECG abnormalities have resolved and that the patient is appropriately monitored. Clinical judgment should be applied.

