5.1.2.2 Management of Increases in QT Interval

Study drug should be discontinued in patients who develop any of the following:

- Sustained (at least two ECG measurements > 30 minutes apart) QTcF that is > 500 ms or > 60 ms longer than the baseline value
- Sustained absolute QTcF that is > 515 ms
- An episode of torsades de pointes or a new ECG finding of clinical concern

Of note, if there is a new intraventricular conduction block, the increase in QRS complex duration should be subtracted from the QTcF change, because this represents an increase in QTcF unrelated to alterations in repolarization. Also of note, it is not uncommon to record arrhythmias, such as non-sustained ventricular tachycardia, supraventricular tachycardia, pauses, or atrial fibrillation, in healthy volunteers receiving placebo during periods of extended ECG monitoring. Therefore, it is critical that expert cardiology advice be sought to confirm any ECG changes and to ascertain the likelihood of a drug-induced arrhythmia versus the background occurrence of this arrhythmia. In such a situation, saving all available ECG data is highly suggested.

Management of patients with sustained QTcF prolongation should include close monitoring, with ECGs repeated at least hourly until two successive ECGs show resolution of the findings, correction of any electrolyte abnormalities, and possible discontinuation of other concomitant medications that are known to prolong the QT interval. Consultation with a cardiologist or electrophysiologist is recommended to help in the management of such patients.

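### Section 4.5.8 lets QTcF monitoring end once readings have stabilized, before the protocol's own more-than-30-minute stopping criterion can be tested

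*Combined protocol and SAP*

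**What the plan says.** The protocol handles a prolonged QTcF in four places.

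- **Section 4.5.8.** Scheduled recordings are single: "A single ECG recording, without artifacts, must be obtained at specified timepoints". If a post-dose QTcF is above 500 ms, or more than 60 ms above baseline, "another ECG must be recorded, ideally within the next 5 minutes, and ECG monitoring should continue until QTcF has stabilized on two successive ECGs". Notice to the Medical Monitor is due within 24 hours, and then: "A decision on study drug discontinuation should be made, as described in Section 4.6.2".
- **Section 5.1.1.7.** This repeats the 4.5.8 procedure, including the *stabilized* end point and the pointer to 4.6.2. It opens with "Management of patients with sustained QTcF prolongation (QTcF that is >500 ms or >60 ms longer than the baseline value" and attaches neither a number of ECGs nor an interval to *sustained*. It closes by also sending the reader to 5.1.2.
- **Section 5.1.2.1, Table 5.** The stopping criterion begins "Sustained (at least two ECG measurements > 30 minutes apart) QTcF" and has the same 500 ms and 60 ms limits. Study drug stops unless another cause is clear.
- **Section 5.1.2.2.** The same criterion appears as "Sustained (at least two ECG measurements > 30 minutes apart) QTcF that is > 500 ms", again with the 60 ms alternative. Patients with sustained prolongation are then followed closely, "with ECGs repeated at least hourly until two successive ECGs show resolution of the findings". A further stop criterion carries no duration condition: "An episode of torsades de pointes or a new ECG finding of clinical concern".

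Section 4.6.2 lists pregnancy, malignancy, serious infection or infection needing an IV antimicrobial, and prohibited medication. It has no QTcF item. The exclusion criteria in 4.1.2 already use a pair of ECGs more than 30 minutes apart for the 440 ms limit at screening.

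**The concern.** The stopping rule needs two readings more than 30 minutes apart. The procedure that generates the readings asks for a prompt repeat and then for stability, which is not recovery. A QTcF that sits steadily above the limit can meet the closing condition of 4.5.8 within minutes, and the pair that the rule needs may never be recorded. Because 5.1.1.7 uses *sustained* without the interval, two sites could also classify the same tracings differently.

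At stake is whether the protocol's objective QTcF criterion is evaluated, and evaluated in the same way everywhere. It does not follow that the patient stays on drug. One reading over the limit already calls for notification and a decision, but those steps rest on judgement.

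**Working it through.** The plan gives no figure to reproduce here. The check compares the texts and adds simple timing arithmetic.

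**1. The rules side by side**

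| Section | Meaning of *sustained* | When monitoring ends | Where the stop decision is sent |
|---|---|---|---|
| 4.5.8 | not used | stabilized, two successive ECGs | 4.6.2 |
| 5.1.1.7 | thresholds only | stabilized, two successive ECGs | 4.6.2, and 5.1.2 for management |
| Table 5 | two or more ECGs, > 30 min apart | not stated | stop rule is here |
| 5.1.2.2 | two or more ECGs, > 30 min apart | resolution on two successive ECGs | stop rule is here |

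**2. Timing under 4.5.8.** Put the triggering ECG at 0 minutes and the repeat at 5 minutes. If the trigger counts as one of the two successive ECGs, monitoring can end at about 5 minutes. If two later ECGs are needed, it can end at about 10 minutes at the same spacing. The stop rule needs more than 30 minutes. At 5-minute spacing the sixth repeat falls at 30 minutes, which is not enough. The seventh, at 7 × 5 = 35 minutes, is the first that would do.

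**3. Two illustrative records** (readings assumed)

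- Baseline 400 ms, then 465 ms at 0 and 10 minutes. The change is 465 − 400 = 65 ms, above 60 ms. The repeat is done and the value is stable, so 4.5.8 allows monitoring to end. Under the 5.1.1.7 wording this is sustained. Under Table 5 it cannot be judged, because no pair is more than 30 minutes apart.
- Readings of 505, 504 and 505 ms at 0, 5 and 10 minutes. All exceed 500 ms and are stable. The outcome is the same.

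**4. Does the hourly rule in 5.1.2.2 supply the missing ECG?** Only on one reading. By that section's own definition, hourly ECGs start once prolongation is already sustained. That requires the later ECG that 4.5.8 never asks for. Under the looser 5.1.1.7 wording they could start at once.

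**5. Where the criterion matters most.** The operative limit is min(500, baseline + 60):

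| Baseline (ms) | Limit (ms) |
|---|---|
| 380 (assumed lower end) | 440 |
| 400 | 460 |
| 420 | 480 |
| 440 (screening limit) | 500 |

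For baselines below 440 ms the 60 ms limb is reached first. At such values, in our judgement, clinical concern is less self-evident than above 500 ms, so the objective rule does more of the work.

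**6. Would a later visit catch it?** This is supporting context only. Read against its day columns, the ECG row of Appendix 1 shows Days −14, 1, 8 and 85 and early termination, with unscheduled ECGs optional. Dosing runs from Day 1 to Day 56, so Days 9 to 56, which is 56 − 8 = 48 of 56 dosing days, have no scheduled ECG. The table layout is partly broken in our copy, but this reading agrees with the vital signs, weight and physical examination rows.

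**The case against.** The strongest reply is that the gap needs a narrow reading. A site would have to apply 4.5.8 alone, take *stabilized* to include stable but still over the limit, and not open 5.1.2.2, whose title is QT management. A stop rule based on two ECGs more than 30 minutes apart implies recording the second, and nothing in 4.5.8 forbids it. The looser wording in 5.1.1.7 errs towards more monitoring.

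Other protections exist. The investigator reviews and signs every tracing and assesses concurrent risk factors. Section 5.1.2.2 urges cardiology advice. Section 4.6.1 allows withdrawal on safety grounds, and the reasons in 4.6.2 are stated not to be exhaustive. The sparse ECG schedule is a separate matter and also limits how often the problem can arise: Day 85 is about four weeks after the last dose, when stopping is moot.

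Much of this stands. The gap is a risk and not a certainty, and the day count shows only that a scheduled visit is unlikely to repair a missed evaluation. Two things are not answered. The protections rest on judgement, so they do not replace the objective criterion. And a site that follows 4.5.8 as written is sent to a section with no QTcF rule and is not sent to the one that has it.

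**Conclusion.** The concern holds, at minor severity. Followed literally, 4.5.8 can close monitoring with QTcF still over the limit and before the Table 5 criterion can be tested. The protocol uses two meanings of *sustained* and two end points for monitoring. The claim is that the criterion can go unevaluated, not that it will, nor that patients will be kept on drug.

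Few patients are expected to be affected, but the documents give no rate of QTcF prolongation, so no number is offered. Sample size, power and the efficacy analyses are unaffected. The conclusion rests on the wording alone. The threshold table also assumes a lower baseline of 380 ms and takes 440 ms as the upper end. The latter is a screening exclusion needing two ECGs, not a formal cap on the baseline value.

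**What to change.** At the next amendment, align 4.5.8 and 5.1.1.7 with the rules already in 5.1.2:

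1. Keep the prompt repeat, and add a required ECG more than 30 minutes after the first abnormal one.
2. Use the Table 5 definition of *sustained* throughout.
3. Replace *stabilized* with the 5.1.2.2 end condition: two successive ECGs showing resolution, that is, back below the thresholds.
4. Point the discontinuation decision to 5.1.2 (Table 5 and 5.1.2.2), alone or together with 4.6.2.

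Every patient who triggers the rule would then have the pair of ECGs it needs. The cost is a short wording change and, for a rare patient, one extra ECG at the same visit. If QTcF has not resolved, the hourly ECGs that 5.1.2.2 already requires for sustained prolongation would follow.

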4.5.9 Patient-Reported Outcomes

Data from two patient reported outcomes (PRO) tools will be collected via questionnaires to document the treatment benefit of fenebrutinib: the Urticaria Patient Daily eDiary, [REDACTED]. The eDiary and [REDACTED], translated into the local language as required, will be completed in their entirety at specified timepoints during the study.

[REDACTED]

Patients will use an electronic device to capture the Urticaria Patient Daily eDiary (see Appendix 3). The electronic device and/or instructions for completing the questionnaires electronically will be provided by the investigator staff. The data will be transmitted to a centralized database maintained by the electronic device vendor. The data will be available for access by appropriate study personnel.

